3.2. Subject Exclusion Criteria

A subject who meets any of the following criteria will be excluded from the study:

1. Treatment with other investigational study drug for any indication for any reason, or receipt of anticancer medications within 28 days before first dose of study drug. Subjects must have recovered (Grade ≤ 1 or at pretreatment baseline) from AEs from previously administered therapies.
2. Untreated brain or central nervous system (CNS) metastases or brain/CNS metastases that have progressed (eg, evidence of new or enlarging brain metastasis or new neurological symptoms attributable to brain/CNS metastases). Subjects with previously treated and clinically stable brain/CNS metastases and who are off all corticosteroids for ≥ 4 weeks are eligible.
3. Known additional malignancy that is progressing or requires active treatment (ie, treatment administered within 3 years). Exceptions include basal cell carcinoma of the skin, squamous cell carcinoma of the skin, carcinoma in situ of the cervix, or other noninvasive or indolent malignancy that has undergone potentially curative therapy.
4. Are pregnant or lactating.
5. Prior receipt of a selective FGFR inhibitor.
6. Abnormal laboratory parameters:
 - a. Total bilirubin $\geq 1.5 \times$ upper limit of normal (ULN; $\geq 2.5 \times$ ULN if Gilbert syndrome or metastatic disease involving liver).
 - b. AST and ALT $> 2.5 \times$ ULN (AST and ALT $> 5 \times$ ULN in the presence of liver metastases).
 - c. Creatinine clearance ≤ 30 mL/min based on Cockcroft-Gault.
 - d. Serum phosphate $>$ institutional ULN.
 - e. Serum calcium outside of the institutional normal range or serum albumin-corrected calcium outside of the institutional normal range when serum albumin is outside of the institutional normal range.
7. History of calcium and phosphate homeostasis disorder.
8. History of human immunodeficiency virus infection.

9. Evidence of hepatitis B virus (HBV) or hepatitis C virus (HCV) active infection or risk of reactivation.
10. History or presence of an abnormal ECG that in the investigator's opinion is clinically meaningful. A screening QTcF interval > 450 milliseconds is excluded.
11. History of clinically significant or uncontrolled cardiac disease, including unstable angina, acute myocardial infarction, New York Heart Association Class III or IV congestive heart failure, or arrhythmia requiring therapy. Subjects with a pacemaker and well-controlled rhythm for at least 1 month before first dose will be allowed.
12. Have undergone major surgical procedure other than for diagnosis within 28 days before Cycle 1 Day 1.
13. Inadequate recovery from toxicity and/or complications from a major surgery before starting therapy.
14. Pregnant or nursing women or subjects expecting to conceive or father children within the projected duration of the study, starting with the screening visit through completion of safety follow-up visit.
15. Concurrent anticancer therapy (eg, chemotherapy, radiation therapy, surgery, immunotherapy, biologic therapy, hormonal therapy, investigational therapy, or tumor embolization).
16. Received prior radiation therapy administered within 4 weeks of first dose of study drug. Subjects must have recovered from all radiation-related toxicities, not require corticosteroids, and not have had radiation pneumonitis. A 2-week washout is permitted for palliative radiation to non-CNS disease.
17. History and/or current evidence of systemic mineral imbalance with ectopic calcification of soft tissues (exception: commonly observed calcifications in soft tissues, such as the skin, kidney, tendons, or vessels due to injury, disease, and aging, in the absence of systemic mineral imbalance).
18. Current evidence of clinically significant corneal (including but not limited to bullous/band keratopathy, corneal abrasion, inflammation/ulceration, and keratoconjunctivitis) or retinal disorder (including but not limited to central serous retinopathy, macular/retinal degeneration, diabetic retinopathy, retinal detachment) as confirmed by ophthalmologic examination.
19. Current use of prohibited medication as described in Section 5.6.2.
20. Use of any potent CYP3A4 inhibitors or inducers within 14 days or 5 half-lives (whichever is shorter) before the first dose of study drug.
21. Known hypersensitivity or severe reaction to INCB054828 or excipients of INCB054828 study drug (refer to the IB).
22. Inability or unlikeliness to comply with the dose schedule and study evaluations, in the opinion of the investigator.
23. Inability to comprehend or unwilling to sign the informed consent form (ICF).

24. Inability or unwillingness to swallow INCB054828 or significant gastrointestinal disorder(s) that could interfere with the absorption, metabolism, or excretion of INCB054828.
25. Subjects who require hemodialysis.
26. Any condition that would, in the investigator's judgment, interfere with full participation in the study, including administration of study drug and attending required study visits; pose a significant risk to the subject; or interfere with interpretation of study data.
27. Subjects with history of hypovitaminosis D requiring supraphysiologic doses to replenish the deficiency. Subjects receiving vitamin D food supplements are allowed.

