 - have not received chemotherapy for metastatic or surgically unresectable urothelial carcinoma due to poor performance status (ie, ECOG performance status of 2) and insufficient renal function (ie, creatinine clearance $<$ 60 mL/min or local guidelines).
- Willingness to avoid pregnancy or fathering children. For subjects in Japan, female subjects who have been amenorrhoeic for at least 12 months resulting from chemotherapy/radiotherapy are considered of childbearing potential and should agree to use adequate contraceptive measures.

Key Exclusion Criteria:

- Treatment with other investigational study drug for any indication for any reason, or receipt of anticancer medications within 28 days before first dose of study drug. Subjects must have recovered (Grade \leq 1 or at pretreatment baseline) from AEs from previously administered therapies.
- Prior receipt of a selective FGFR inhibitor.
- Abnormal laboratory parameters:
 - Total bilirubin \geq 1.5 \times upper limit of normal (ULN; \geq 2.5 \times ULN if Gilbert syndrome or metastatic disease involving liver).
 - Aspartate aminotransferase (AST) and alanine aminotransferase (ALT) $>$ 2.5 \times ULN (AST and ALT $>$ 5 \times ULN in the presence of liver metastases).
 - Creatinine clearance \leq 30 mL/min based on Cockcroft-Gault.
 - Serum phosphate $>$ institutional ULN.
 - Serum calcium outside of the institutional normal range or serum albumin-corrected calcium outside of the institutional normal range when serum albumin is outside of the institutional normal range.
- Use of any potent CYP3A4 inhibitors or inducers within 14 days or 5 half-lives (whichever is shorter) before the first dose of study drug.
- Known hypersensitivity or severe reaction to INCB054828 or excipients of INCB054828 study drug.
- Inability or unwillingness to swallow INCB054828 or significant gastrointestinal disorder(s) that could interfere with the absorption, metabolism, or excretion of INCB054828.
- Subjects who require hemodialysis.

INCB054828/Study Drug, Dosage, and Mode of Administration:

INCB054828 will be self-administered as a QD oral treatment on a 2-weeks-on-therapy and 1-week-off-therapy schedule or continuous dose regimen (no planned dose holiday). In both dosing schedules subjects will be administered INCB54828 at a starting dose of 13.5 mg. Each dose of study drug should be taken as soon as possible upon rising, with or without food.

Reference Therapy, Dosage, and Mode of Administration: Not applicable.

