3. SUBJECT ELIGIBILITY

Deviations from eligibility criteria are not allowed because they can potentially jeopardize the scientific integrity of the study, regulatory acceptability, and/or subject safety. Therefore, adherence to the criteria as specified in the Protocol is essential.

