5.4.2. Criteria and Procedures for Dose Interruptions and Adjustments of Study Drug

Treatment with INCB054828 may be delayed up to 14 days to allow for resolution of toxicity. Subjects may resume treatment if no medical condition or other circumstance exists that, in the opinion of the investigator, would make the subject unsuitable for further participation in the study. The treating investigator should contact the sponsor to discuss the case of any subject whose treatment has been delayed for more than 14 days before restarting treatment with INCB054828.

For subjects who present with possible or confirmed serous retinal detachment/retinal pigmented epithelium detachment (SRD/RPED) based on OCT, the guidelines in [Table 2](#) should be followed. It is recommended to discuss the findings with the Incyte medical monitor before making changes to the subject's treatment.

Per CTCAE v4.03, retinal detachment is graded as Grade 3 (macular sparing) and Grade 4 (macula-off), but this refers to rhegmatogenous retinal detachment (when a hole occurs in the retina). There is no grading for SRD/RPED (there is no hole in the macula, just fluid accumulation). Therefore, grading should be based on retinopathy.

Because subjects may enter the study with extensive pretreatment toxicities, these dose reduction rules are provided as guidelines (see [Table 2](#)). Individual decisions regarding dose reduction should be made using clinical judgment and in consultation with the sponsor's medical monitor, taking into account relatedness of the AE to the study drug and the subject's underlying condition. Adverse events that have a clear alternative explanation or transient (≤ 72 hours) abnormal laboratory values without associated clinically significant signs or symptoms may be exempt from dose-reduction rules.

Table 2: Guidelines for Interruption and Restarting of Study Drug

ADVERSE EVENT	ACTION TAKEN
Chemistry	

 AST and/or ALT > 5.0 × ULN Note: In subjects with bone metastasis-related elevations at baseline, contact sponsor to discuss clinical management and possible dose reductions.	Step 1: Interrupt study drug up to 2 weeks (14 days) until the toxicity has resolved to ≤ Grade 1 except by approval of the medical monitor. Step 2: If assessed as related to study drug, restart study drug at the next lower dose; monitor as clinically indicated.
Other toxicities	

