6.2. Treatment

The treatment period begins on the day the subject receives the first dose of study drug (Cycle 1 Day 1) through the point at which the investigator determines the subject will be permanently discontinued from study drug (EOT). Cycle 1 Day 1 must be no more than 28 days after the subject has signed the ICF and no more than 3 days after the subject is enrolled. Dates for subsequent study visits will be determined based on this day and should occur within 3 days (\pm) of the scheduled date unless delayed for safety reasons. At Cycle 1 Day 1, results from screening visit evaluations should be reviewed to determine whether the subject continues to meet the eligibility requirements, as specified in Section 3.

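### Exclusion 6b joins AST and ALT with *and*, so as worded one raised enzyme alone does not exclude; it should say *or* (low severity, wording only)

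*Protocol*

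**What the plan says.** Section 3.2 lists the exclusion criteria, and meeting any one of them excludes. Criterion 6 covers laboratory values. Within it, 6b sets a transaminase limit of 2.5 × ULN, raised to 5 × ULN for subjects with liver metastases ("ULN in the presence of liver metastases"). At both limits the enzymes are joined by *and*; the link between the two limits reads "ULN (AST and ALT". The synopsis, under Key Exclusion Criteria, has the same limits and the same conjunction: "Aspartate aminotransferase (AST) and alanine aminotransferase (ALT").

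Three other places bear on how 6b is read:

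- Section 3 does not allow eligibility deviations and states that "adherence to the criteria as specified in the Protocol is essential".
- Section 5.4.2, Table 2, interrupts study drug during treatment for "AST and/or ALT > 5.0 × ULN".
- Section 6.2 requires a check at Cycle 1 Day 1, when "results from screening visit evaluations should be reviewed to determine whether the subject continues to meet the eligibility requirements" in Section 3.

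**The concern.** An exclusion that requires A and B to exceed a limit is met, on its plain wording, only when both do. For a hepatic safety criterion that is the permissive direction: one enzyme may be at any level so long as the other is within its limit. The dosing rule for the same two enzymes spells out *and/or*, and 6e, in the same laboratory list, joins its two calcium tests with *or* ("Serum calcium outside of the institutional normal range or serum albumin-corrected calcium outside of the institutional normal range"). A site told to follow the criteria as specified therefore has some ground for taking the *and* in 6b at face value.

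What is at stake is consistency and safety at entry. Two sites could classify the same subject differently, and a subject with one markedly raised enzyme could start dosing without breaching any numeric transaminase criterion.

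**Working it through.** There is no figure in the plan to reproduce. The check applies 6b to example subjects under each reading.

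**Inputs.** Limit L = 2.5 × ULN without liver metastases and 5 × ULN with them (Section 3.2, 6b; same in the synopsis). The enzyme values are illustrations, not frequencies.

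**Rules.**
- Literal reading: excluded if ALT > L and AST > L.
- Either-enzyme reading: excluded if ALT > L or AST > L.

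| Liver metastases | ALT (× ULN) | AST (× ULN) | L | ALT > L | AST > L | Literal | Either-enzyme |
|---|---|---|---|---|---|---|---|
| No | 6.0 | 2.0 | 2.5 | yes | no | not excluded | excluded |
| Yes | 6.0 | 2.0 | 5.0 | yes | no | not excluded | excluded |
| Yes | 6.0 | 4.0 | 5.0 | yes | no | not excluded | excluded |
| No | 2.0 | 3.0 | 2.5 | no | yes | not excluded | excluded |

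**Ceiling implied for a single enzyme.** Literal: none, provided the other enzyme is at or below 2.5 × ULN (5 × ULN with liver metastases). Either-enzyme: 2.5 × ULN, or 5 × ULN with liver metastases.

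**Fit with Table 2.** On the either-enzyme reading, the highest value allowed at entry with liver metastases is 5.0 × ULN. Table 2 acts above 5.0 × ULN, and 5.0 > 5.0 is false, so the entry limit and the on-treatment trigger meet without overlapping. That neat fit is a reason to think the either-enzyme meaning was intended.

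**Does anything else settle it?**
- The lead-in to Section 3.2 joins the criteria to one another. It does not say how the enzymes combine inside 6b.
- Exclusion 1 requires recovery from adverse events of earlier therapy to Grade 1 or less, or to pretreatment baseline. It sets no fixed transaminase limit and does not reach disease-related elevations.
- Exclusion 9 deals with hepatitis B and C, and 6a with bilirubin. Neither limits AST or ALT.
- Exclusion 26 lets the investigator exclude for conditions that could "pose a significant risk to the subject", which is a judgment with no number attached.
- The Cycle 1 Day 1 check applies the Section 3 wording again, so it carries the same ambiguity.

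**The case against.** The best reply is that nobody would read 6b literally, because this protocol uses *and* loosely. Section 5.6.2 prohibits potent CYP3A4 inhibitors *and* inducers, which cannot mean only the combination, and exclusion 20 covers the same potent agents with *or*. Exclusion 7 pairs calcium and phosphate with *and* and is naturally read as either. The calcium criterion 6e is a weak comparator, since its *or* joins two ways of assessing one analyte rather than two analytes sharing a limit. Other controls also reduce the practical risk: exclusions 1, 9 and 26, the bilirubin limit, serum chemistry on Cycle 1 Days 1, 8 and 15, and Table 2 acting on either enzyme once treatment has begun.

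Most of this stands. The loose usage makes the either-enzyme meaning almost certain, and the other controls make harm less likely. What remains is that neither document states that meaning for eligibility and none of those controls puts a transaminase limit at entry. A numeric safety exclusion should not depend on the reader correcting its conjunction.

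A reader might also infer that the protocol admits subjects who would need immediate interruption under Table 2. It does not follow. Section 5.4.1 ties interruptions to toxicities that occur, and Section 8.1.2 sends conditions already present at consent to Medical History, so a pre-dose value above 5 × ULN is not in itself a Table 2 event.

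**Conclusion.** The point holds as a low-severity wording correction to a safety criterion. As written, 6b and the synopsis do not exclude a subject with only one enzyme above the limit. The intended rule is almost certainly the stricter one.

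The documents do not support going further. They do not show that anyone was enrolled on the literal reading, and they give no baseline AST or ALT distribution from which to estimate how many could have been. Nor is there a basis for inferring bias in the primary result: efficacy-evaluable status turns on a centrally confirmed alteration and at least one dose, and no effect on ORR, sample size or power is claimed. The conclusion rests only on the ordinary meaning of *and* in an exclusion criterion and on the absence of any clarifying text in the protocol or SAP.

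**What to change.** In exclusion 6b and in the synopsis, replace *and* with *or* between the enzymes at both limits, so that the rule reads: AST or ALT > 2.5 × ULN (AST or ALT > 5 × ULN with liver metastases). Table 2 needs no change.

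The cost is four one-word edits at the next amendment and a note to sites, with no added procedure or data. The documents do not say whether enrollment is complete; if it is, the practical benefit is smaller.

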5.6.2. Prohibited Medications

The following medications and measures are prohibited:

- The concomitant administration of potent CYP3A4 inhibitors and inducers and moderate CYP3A4 inducers is prohibited. Based on the low overall bioavailability of topical ketoconazole, there are no restrictions on topical ketoconazole.
- Any concomitant use of a selective FGFR inhibitor is prohibited.
- Investigational study drug for any indication is prohibited.
- Use of any anticancer medications other than the study medication from 21 days before Day 1 is prohibited.

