#### **5.3.2. Per Protocol Population**

Subjects in the efficacy evaluable population who are considered to be sufficiently compliant with the Protocol compose the PP population.

The following procedures will be performed to identify those subjects who are to be excluded from the PP population before the database freeze:

- Clinical review of Protocol deviations/violations.
- Clinical review of concomitant medications as defined in Section 5.6 of the Protocol.
- Clinical review of the dose administration and drug accountability listing.

The determination of subjects being considered for exclusion from the PP population by the clinical team will be prepared and signed before database freeze.

The PP population will be used in the supportive sensitivity analyses for efficacy endpoints.

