##### **7.2.1.2. Overall Response Rate and Best Response**

A subject is considered an objective responder if they have a best overall response of CR or PR at any postbaseline visit prior to first PD.

In general, best overall response is the best response recorded postbaseline prior to and including the first PD, in the order of CR, PR, SD, PD, and NE. A best overall response of CR or PR needs to be confirmed, and confirmation method is described in the Independent Review Charter. In the case of SD, measurements must meet the SD criteria at least once after the date of first

dose at a minimum interval of 49 days. Subjects that fail to meet this criterion will have best overall response of PD if the next available assessment indicates PD or NE if there is no additional assessment available.

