#### **7.4. Other Efficacy Analyses**

##### **7.4.1. Largest Percentage Reduction in Sum of Diameters of Target Lesions**

For subjects with measurable lesions at baseline, target lesion sizes will be measured by sum of diameters. The best percent change from baseline, defined as the largest decrease in target lesion size during the study, will also be summarized, and a waterfall plot of best percent change will be generated.

Target lesions considered "too small to measure" will be assigned a default value of 5 mm for purposes of this analysis. Likewise, target lesions identified as "not present" at postbaseline assessments will be assigned 0 mm for this analysis. In the event a target lesion is unaccounted for in a particular postbaseline timepoint (ie, the assessment is missing or NE), then the overall sum of diameters for target lesions will not be evaluable for that postbaseline timepoint.

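### The primary ORR has no cut-off at other anticancer therapy, although PFS and DOR do, and the plan never says whether on-study local therapy counts as such

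*Protocol*

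**What the plan says.** **Entry.** Protocol 3.2, criterion 15, excludes subjects with "Concurrent anticancer therapy (eg, chemotherapy, radiation therapy, surgery, immunotherapy, biologic therapy, hormonal therapy, investigational therapy, or tumor embolization". So radiation, surgery and embolization are classed as anticancer therapy. Eligibility is checked at screening and once more before dosing: "At Cycle 1 Day 1, results from screening visit evaluations should be reviewed to determine whether the subject continues to meet the eligibility requirements" (Protocol 6.2). No later check is described.

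**On treatment.** Protocol 5.6.2 opens with "The following medications and measures are prohibited", but every item under it is a drug. Its general anticancer item is "Use of any anticancer medications other than the study medication from 21 days before Day 1 is prohibited". The withdrawal criteria in 5.5.1 do not mention local therapy.

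**Scanning.** The synopsis ends RECIST assessment when new anticancer therapy starts, and Protocol 6.4.3 moves a subject who starts one into survival follow-up. Sections 6.4.2 and 7.6.1 use the same stopping event, but for subjects who have left treatment. For subjects on drug, 7.6.1 and Table 4 schedule scans every 9 weeks and name no stop for local therapy.

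**Analysis.** In SAP 7.2.1.2, "best overall response is the best response recorded postbaseline prior to and including the first PD, in the order of CR, PR, SD, PD, and" finally not evaluable. CR and PR must be confirmed by a method set out in the Independent Review Charter. SAP Table 1 censors PFS at the last adequate assessment before new anticancer treatment, and SAP 7.3.4 applies the same algorithm to DOR.

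**The concern.** The ORR rule and the PFS and DOR rules treat the same event differently. For PFS and DOR, what is seen after new anticancer treatment is no longer evidence about the study drug. For the primary endpoint there is no such limit.

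The primary analysis is a single-arm ORR in Cohort A-CD with no control group. Shrinkage caused by another therapy would be credited to INCB054828. The error runs one way: best overall response takes the best category over a set of assessments, so admitting more assessments before first PD can add responders and cannot remove them.

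Local therapy is where the gap is most likely to matter. Other anticancer drugs are banned on treatment. Local therapy is classed as anticancer at entry but is not named in the on-treatment ban.

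**Working it through.** **1. The plan's own figure.** Inputs from Protocol 9.2 and SAP 3.2 and 7.2.1: ORR 35%, about 100 subjects, 10% lost to follow-up, lower limit above 25%, two-sided 95% Clopper-Pearson interval. The lower limit for x responders of n is the 2.5% quantile of Beta(x, n − x + 1).

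- 35/100: 25.73% (upper limit 45.18%).
- n = 90 after 10% loss: 35% of 90 is 31.5 responders. The non-integer calculation gives 25.24%; in whole subjects, 32/90 gives 25.74% and 31/90 gives 24.74%.

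The stated figure reproduces, though only just at n = 90.

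**2. The rules applied to one subject (illustrative dates on the 9-week schedule).** SD at week 9; new anticancer treatment at week 12; PR at week 18, confirmed at week 27; no progression.

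| Endpoint | Rule | Result |
|---|---|---|
| ORR | Best response before first PD (SAP 7.2.1.2) | Responder |
| PFS | Last adequate assessment before new treatment (SAP Table 1) | Censored at week 9 |
| DOR | Starts at first response; censored as PFS (SAP 7.3.4) | Starts week 18, censored week 9 |

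The duration is 9 − 18 = −9 weeks. Followed as written, the rules give this subject a response with a negative duration.

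**3. Is local therapy new anticancer treatment?** Criterion 15, the synopsis and Protocol 6.4.3 taken together suggest yes, and that scanning should then end. Protocol 5.6.2 (drugs only), 7.6.1 and Table 4 (scans continue on drug) point the other way or are silent. The wording also varies: therapy in the synopsis and 6.4.3, antineoplastic therapy in 6.4.2, treatment in SAP Table 1. None of these terms is defined.

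**4. Effect of one subject.** At the threshold, removing one misattributed response changes 35/100 (25.73%) to 34/100 (24.82%), or 32/90 (25.74%) to 31/90 (24.74%).

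**5. Effect of a rate (assumed).** The documents give no frequency of on-study local therapy. Let f be the share of true non-responders counted as responders. The apparent ORR is p + (1 − p)f; for example 0.25 + 0.75 × 0.05 = 0.2875. The lower limit exceeds 25% from 35 responders at n = 100, so the chance of that is P(X ≥ 35).

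| f (assumed) | True 25%: apparent ORR | P(X ≥ 35) | True 30%: apparent ORR | P(X ≥ 35) |
|---|---|---|---|---|
| 0% | 25.00% | 1.6% | 30.0% | 16.3% |
| 1% | 25.75% | 2.5% | 30.7% | 20.4% |
| 3% | 27.25% | 5.4% | 32.1% | 30.0% |
| 5% | 28.75% | 10.3% | 33.5% | 41.2% |

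**The case against.** The strongest reply is that the protocol already ends assessment in these cases. The synopsis stop is not limited to subjects off drug, criterion 15 calls local therapy anticancer, and its word concurrent, with no time window, can be read as reaching into the treatment period. Criterion 14 shows that the exclusion list can do so. This is a fair reading, so it would be wrong to infer that the plan permits local therapy on drug and keeps scanning. But 7.6.1 and Table 4 do not carry the stop, the term is undefined, and an instruction about when to scan is not an analysis rule: a scan that exists before first PD still counts under SAP 7.2.1.2.

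Second, responses are read centrally and must be confirmed. The charter may deal with treated lesions, and that cannot be checked here. The SAP cites it only for confirmation, and confirmation does not exclude lasting shrinkage from another therapy.

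Three further inferences go beyond the text:

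- *That a resected lesion is scored as zero in the primary ORR.* SAP 7.4.1 says lesions recorded as not present "at postbaseline assessments will be assigned 0 mm for this analysis". That analysis is the best percent change and waterfall plot; nothing feeds it into the central response.
- *That the per-protocol analysis must miss these cases.* One of its reviews is "Clinical review of concomitant medications as defined in Section 5.6 of the Protocol", which names no local therapy, but SAP 5.3.2 also reviews protocol deviations. Whether local therapy is a deviation depends on the unsettled reading, so capture is uncertain rather than ruled out.
- *That crossing 25% decides the trial.* SAP 3.1 calls all analyses exploratory and 7.1 states no hypothesis. The 25% value appears in the sample-size and futility text. Any single misclassification would move the limit as much.

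**Conclusion.** The inconsistency stands on the SAP's own text: ORR has no cut-off at other anticancer therapy, PFS and DOR do, and the combination can place a DOR censoring date before the response. Whether on-study local therapy triggers any of these rules is unsettled, because the protocol passages point in different directions and the term is undefined.

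The direction of any error is upward. Its size is unknown: the 0% to 5% range above is an assumption, and the charter may narrow the problem. What can be said firmly is that the design target has little slack, since one responder at n = 100 separates a lower limit of 24.8% from 25.7%. The point deserves correction because the primary endpoint is affected and the remedy is short; the documents do not show that the ORR will be biased.

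**What to change.** 1. Define new anticancer therapy once in the SAP, consistently with criterion 15 and including local therapy to tumor lesions. Use that definition in Table 1, DOR and ORR.
2. In SAP 7.2.1.2, limit best overall response to assessments up to the earlier of first PD and the start of new anticancer therapy. Keep the subject in the denominator. Report ORR without the cut-off as a sensitivity analysis. A date cut-off is preferable to judging whether a response depends on the treated lesion, which would need a central re-read. State whether a confirming scan must also fall before the cut-off; read literally, it must.
3. Apply the same cut-off to best percent change in SAP 7.4.1.
4. Name on-study procedures in the per-protocol review in SAP 5.3.2.
5. Reconcile Protocol 3.2 (criterion 15), 5.6.2, the synopsis, 6.4.3 and 7.6.1. Which local procedures are permitted is for the clinical team.

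**Cost.** A few SAP sentences and a protocol clarification. No new data are needed, because Protocol 7.4 already records concomitant procedures in the eCRF. The ORR may be slightly lower, and a genuine drug response first seen after palliative local therapy to another site would not count in the primary analysis; the sensitivity analysis would show it.
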